Randomization: Decreases the chance of an imbalance in subject characteristics (for example age, BMI, or duration of T1DM) between treatment groups, as there may be differences in pancreatic β -cell function at presentation of T1DM, rate of decline of residual β -cell function early after diagnosis, and severity of autoimmunity at different ages.

Treatment allocation 2:1 (2 active, 1 placebo) enables evaluation of safety of CFZ533 (first-in-pediatrics) and assessment of the risk-benefit of CFZ533 in pediatric subjects with new onset T1DM, optimizing exposure to obtain safety data for CFZ533 and minimizing exposure to placebo with attendant study burden.

Treatment duration: One year of treatment is required to be able to differentiate potential drug effect on reduction in β -cell function (slowing of the decline) from the natural disease progression, over a clinically relevant duration of time ([Ehlers 2016](#)).

Follow-up duration: Subjects will be followed CCI from the last dose of study drug to ensure health during drug pharmacokinetic and pharmacodynamic elimination. Follow-up observation CCI from the last dose of study drug permits assessment of the elimination of CFZ533 down to plasma levels that are expected to have no pharmacodynamic (PD) effects in tissues, and safety monitoring. Up to 20 weeks of follow-up is planned (with last dose of CFZ533 or placebo administered CCI), which permits monitoring of durability of effect on the primary endpoint of β -cell preservation, approximately 20 weeks post treatment.

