12.5.1 Efficacy and/or Pharmacodynamic endpoint(s)

Data for the secondary variables (*i.e.* total daily dose of insulin, insulin-dose adjusted HbA1c) will be descriptively summarized for each treatment group and each time point (where applicable).

Full remission will be defined by HbA1c $\leq 6.5\%$ (48 mmol/mol) and no exogenous insulin use, at 52 weeks (1 year). Two validated criteria will be used to assess partial remission including proportion of subjects with (1) Insulin Dose Adjusted HbA1c (IDAA1c) ≤ 9.0 (Mortensen et al 2009) and (2) HbA1c $< 7.0\%$ (53 mmol/mol) and total daily insulin dose < 0.5 units per kg per day (Couper and Donaghue 2009). Stimulated C-peptide AUC by MMTT at Week 72 will be analyzed in the same manner as the primary objective. The baseline*visit interaction term may also be considered for this model due to the follow-up.

The proportion of subjects with detectable C-peptide, rate of decline from baseline C-peptide, and time to undetectable C-peptide will be descriptively summarized with estimates and confidence intervals for each treatment group and each time point (where applicable).

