6.1.2 Descriptive analyses

Normalized stimulated C-peptide AUC (Weeks 12, 24, 36 and 52 on treatment and Week 72), its change and percent change from baseline will be listed by treatment, subject and visit. Summary statistics will be provided for raw value, change and percent from baseline by treatment and visit/time and will include mean (arithmetic), SD, CV (arithmetic), median, minimum and maximum. In addition, geometric mean/CV will be provided for raw value.

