6.1.2.1 Graphical presentation of results

Geometric mean (80% CI) of normalized stimulated C-peptide AUC and ratio to baseline will be plotted by visit and treatment. Spaghetti plots of normalized stimulated C-peptide AUC and percent change from baseline of all individuals will be given by treatment.

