6.1.3 Statistical model, assumptions and hypotheses

The primary statistical analysis will be done using the Full analysis set (treatment policy estimand). As a secondary analysis, the model will be run using the Per Protocol set (hypothetical strategy estimand). For both analyses, all data collected for subjects in the respective analysis sets will be used in the model (e.g. including data after study drug discontinuation). Stimulated C-peptide AUC by the standard MMTT, normalized by the duration of measurements, will be analyzed with a mixed model repeated measures (MMRM) analysis. The natural log of the AUC (Weeks 12, 24, 36 and 52 on treatment) will be the dependent variable in this analysis. Independent variables will include age group (≥ 12 to < 18 , ≥ 18 to 21) treatment, visit, and the treatment by visit interaction.

The natural log of the baseline AUC will be used as a covariate and subject will be used as a random effect. Back transformation (exponential) will be used to obtain the least square geometric mean of each treatment, the ratio of CFZ533 to placebo, the 80% confidence interval of the ratio, and the one-sided p-value of treatment benefit for each time point. The model-based estimated fixed effects and p-values will be presented, along with the overall treatment effect.

Note 1: Any C-peptide AUC collected at a post-baseline unscheduled visit will be assigned to the closest scheduled visit for the model-based analysis; in the case of a tie it will be assigned to the previous visit (e.g. unscheduled collected at Week 30 will be assigned to Visit 24 for the model-based analysis). If a C-peptide AUC is already available at the scheduled visit, the average of the scheduled and unscheduled visit AUC will be used in the model.

Note 2: Week 52 C-peptide AUC which was not actually collected 365 +15 days after the first dose (i.e. due to it being the EOT assessment for early treatment discontinuation) will not be used for the model-based analysis as a Week 52 assessment, but will be assigned to the closest visit.

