6.2.1 Variables

- Normalized stimulated C-peptide AUC_{0-2 hrs} by MMTT at Week 72.
- Average of Total daily dose of insulin

Total daily dose of insulin for a given day is the total daily units of insulin (adding insulin pump total basal units per day, insulin pump total bolus units per day and total units insulin injection (syringe) units per day) adjusted per body weight (unit/Kg/24 h). This information will be recorded at the site for at least 3 days and up to 7 days prior to each visit, as available (See Site Operations Manual). The average of total daily units of insulin per day (at each visit) will be calculated.

- Insulin-dose adjusted HbA1c (IDAA1c) ([Andersen et al 2014](#)).

IDAA1C = HbA1C (percent) + 4 × [insulin dose (units per kg per day)].

If HbA1c is stated in mmol/mol, it can be converted to percent by the following formula:
HbA1c % = (HbA1c mmol/mol × 0.0915) + 2.15.

- Remission at 52 weeks defined by meeting any of the below criteria:
 - Full remission defined by HbA1c ≤ 6.5% (48 mmol/mol) and no exogenous insulin use at 52 weeks.
 - Partial remission defined by Insulin Dose Adjusted HbA1c (IDAA1c) ≤ 9.0 ([Mortensen et al 2009](#))
 - Partial remission defined by HbA1c < 7.0% (53 mmol/mol) and total daily insulin dose < 0.5 units per kg per day ([Couper and Donaghue 2009](#)).
- The proportion of subjects with detectable C-peptide and time to undetectable C peptide. Undetectable C-peptide is defined as all timed values on the MMTT below the LLOQ.
- The proportion of subjects with Peak C-peptide ≥ 0.2 pmol/mL and time to Peak C-peptide < 0.2 pmol/mL (or below LLOQ)
- Rate of decline from baseline C-peptide

A linear mixed model regression of the log transformed stimulated C-peptide AUC, including baseline assessment, on time expressed in years (time = 1 at Week 52 and 0 at baseline) will be performed. The mixed model will include treatment effect, time by treatment interaction with time as continuous variable and subject as random effect. The estimates of the yearly rate of decline by treatment and their 80% confidence intervals will be obtained after back transformation (exponential) of the estimates of the slopes.

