6.2.3 Statistical model, assumptions and hypotheses

Normalized stimulated C-peptide AUC by MMTT at Week 72 will be analyzed in the same manner (and using the same model) as the primary objective. C-peptide AUC at all time points up to and including Week 72 will be included. The baseline by visit interaction term may also be considered for this model.

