6.2.3.1 Model checking procedures

Model checking procedures for stimulated C-peptide AUC by MMTT at Week 72 will be the same as for primary analysis, refer to [Section 6.1.3.1](#).

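### The C-peptide models name subject as the only random effect; if decline rates vary between subjects, the 80% intervals at Weeks 52 and 72 and for the decline rates are too narrow

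*SAP*

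**What the plan says.** The primary analysis (Protocol 12.4.2, SAP 6.1.3) is called a mixed model repeated measures analysis of log C-peptide AUC. SAP 6.1.3 includes Weeks 12, 24, 36 and 52. The fixed effects are age (age group in the SAP), treatment, visit and treatment by visit. The rest of the model is given in one sentence: "The natural log of the baseline AUC will be used as a covariate and subject will be used as a random effect".

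SAP 6.2.3 states that Week 72 AUC "will be analyzed in the same manner (and using the same model) as the primary objective", with all visits up to Week 72 included and an optional baseline-by-visit term.

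The rate of decline (SAP 6.2.1) is a linear regression of log AUC on continuous time: "The mixed model will include treatment effect, time by treatment interaction with time as continuous variable and subject as random effect". It yields a yearly decline with an 80% interval for each arm.

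SAP 6.1.3.1, headed as model checking, deals only with missing data. SAP 6.2.3.1 refers back to it: "Model checking procedures for stimulated C-peptide AUC by MMTT at Week 72 will be the same as for primary analysis". The descriptive outputs include by-visit variability ("In addition, geometric mean/CV will be provided for raw value") and individual profiles ("Spaghetti plots of normalized stimulated C-peptide AUC and percent change from baseline of all individuals will be given by treatment"). The legible text names no covariance structure, random slope, robust variance or degrees-of-freedom method.

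**The concern.** A subject random effect alone gives compound symmetry: equal variance at every visit and equal correlation between every pair of visits. When subjects decline at different rates, the variance left after baseline adjustment grows with time, and a pooled variance averages the early and late visits. The decline-rate model goes further. Without a random slope, it attributes all departures from the arm's common slope to independent residual error.

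Protocol 12.4.2 examines the primary objective with the Week 52 result of this model, reported as a ratio, an 80% interval and a one-sided p-value. Protocol 1.2 says the study is to inform the design of confirmatory trials. With varying slopes, the Week 52 and Week 72 results would look more precise than they are, and the early visits less precise.

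**Working it through.** **1. The plan's own figure.** Protocol 12.8.1 uses CV 70%, 36 evaluable subjects at 2:1 (24 and 12) and one-sided alpha 0.1.
- SD of log AUC = sqrt(ln(1 + 0.7²)) = 0.631.
- SE = 0.631 × sqrt(1/24 + 1/12) = 0.223.
- Normal approximation: 55.8% power at ratio 1.375 and 76.1% at 1.56. Noncentral t on 34 df: 55.1% and 75.4%.

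The stated 55% and 75% are reproduced. They rest on a single-time-point SD, so the repeated-measures covariance does not affect them.

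**2. Direction, in closed form.** With complete data, a random-intercept model assigns every visit the mean of the visit variances. With t in years (week/52), the baseline-adjusted variance at visit v is

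var(v) = c + σe² + σs² t², where c = σ0² σe² / (σ0² + σe²),

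and model SE / true SE = sqrt(mean variance / var(v)).

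t² at Weeks 12, 24, 36, 52 and 72 is 0.05, 0.21, 0.48, 1.00 and 1.92. The mean is 0.44 over the four primary visits and 0.73 with Week 72 added. Week 36 is close to the primary-model mean, Week 52 lies well above it, and Weeks 12 and 24 lie below it.

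Example with assumed σs = 0.4, σe = 0.25, σ0 = 0.55:
- c = 0.3025 × 0.0625 / 0.365 = 0.052, so var(v) = 0.114 + 0.16 t².
- Primary model, Week 52: mean variance 0.184, own variance 0.274, SE ratio 0.82. Coverage = 2Φ(1.2816 × 0.82) − 1 = 71%.
- Week 72 model, Week 72: mean variance 0.231, own variance 0.421, SE ratio 0.74, coverage 66%.

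**3. Size, by simulation.** From the plan: 44 subjects (29:15), 8 dropouts before Week 52, Week 52 log-AUC SD 0.63. Assumed: slope SD 0-0.5 log units/year and residual SD 0.15-0.25. The true treatment effect is null. REML was used, with 5,000 trials per scenario for the Week 52 model and 4,000 for each of the others. The Monte Carlo SE of coverage is about 0.6-0.8 points.

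To interpret the slope SDs: the protocol's mean decline from 0.7 to 0.4 is ln(0.4/0.7) = −0.56. One SD either side of it means a one-year AUC loss of 37-48% at slope SD 0.1, 30-53% at 0.2, 23-58% at 0.3 and 6-65% at 0.5.

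Coverage (%) of the 80% interval, subject random intercept only:

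| Slope SD / residual SD | Wk 12 / 24 / 36 | Wk 52 | Wk 52 one-sided rejection | Wk 72 | Decline, placebo / active |
|---|---|---|---|---|---|
| 0 / 0.20 | not tabulated | 80.7 | 9.4 | 78.9 | 80.6 / 79.0 |
| 0.1 / 0.15 | not tabulated | 77.5 | 11.3 | 75.2 | 76.0 / 75.4 |
| 0.1 / 0.25 | not tabulated | 78.2 | 10.8 | 77.4 | 77.0 / 78.4 |
| 0.2 / 0.15 | 85.5 / 82.6 / 78.8 | 71.8 | 14.0 | 67.2 | 68.7 / 69.0 |
| 0.2 / 0.25 | 82.8 / 81.1 / 79.0 | 76.2 | 11.6 | 73.2 | 73.7 / 72.9 |
| 0.3 / 0.15 | 89.3 / 85.4 / 77.5 | 67.8 | 16.6 | 62.6 | 61.6 / 61.9 |
| 0.3 / 0.25 | 85.2 / 82.5 / 78.5 | 72.1 | 14.1 | 67.1 | 68.7 / 68.9 |
| 0.5 / 0.15 | 95.0 / 86.9 / 76.4 | 61.6 | 19.6 | 58.3 | 54.7 / 54.6 |
| 0.5 / 0.25 | 90.7 / 86.2 / 79.0 | 66.9 | 15.9 | 61.7 | 62.1 / 61.2 |

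A separate simulation at slope SD 0.4 and residual SD 0.25 gave 70% at Week 52, 63% at Week 72 and 63-67% for the decline rates. The directions held for slope SDs of 0.2-0.6 and intercept-slope correlations from −0.4 to +0.4.

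**4. The same trials with the covariance modelled.** An unstructured covariance covers 79-80% at Week 52 and 79-81% at Week 72. Kenward-Roger changes coverage by at most 0.5 points. With a random slope, the decline-rate intervals cover 79-81% (81-83% at slope SD 0).

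**The case against.** The strongest reply is that this is under-specification, not error. Both documents call the primary analysis an MMRM, many statisticians would fit that with an unstructured covariance, and programming specifications or redacted text may say so. If so, the visit-model part disappears. This stands as a condition. But the text adds a subject random effect, which points to a random intercept, so two analysts could fit different models from it. The reply does not reach the decline-rate model, which is not called an MMRM.

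The documents also give little evidence that slopes vary. Protocol 4.1 lists the rate of decline among features that may differ with age, as a reason to randomize. It also says that progression up to age 21 resembles that of adolescents. Age is in the visit models, though only as a main effect. Slope SD 0.5 is extreme: it would account for 0.25/0.399 = 63% of the Week 52 variance, so the lowest coverages should not carry the argument. At slope SD 0.2 with residual SD 0.25, Week 24 coverage is 81%, hardly distinguishable from nominal.

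The optional baseline-by-visit term at Week 72 would absorb slope variation related to baseline, but not independent variation. The planned tables would expose a large slope SD: at 0.5 the expected geometric CV goes from 42% at Week 12 to 70% at Week 52 and 93% at Week 72. A moderate one would be hard to see: at 0.2 the figures are 66%, 70% and 74%. No action is tied to these outputs.

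The consequences are limited. The trial is non-confirmatory, and Protocol 12.5.1 makes the decline rate descriptive: "rate of decline from baseline C-peptide, and time to undetectable C-peptide will be descriptively summarized with estimates and confidence intervals".

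**Conclusion.** The concern holds. As written, the three models have a random part that gives valid intervals at each visit and for the decline rates only if decline rates do not vary between subjects. The direction follows from algebra; the size depends on a slope SD that the documents do not give. For slope SDs of 0.2-0.3, coverage of the 80% interval is 68-76% at Week 52, 63-73% at Week 72 and 62-74% for the decline rates, and one-sided rejection at Week 52 is 12-17% instead of 10%. At 0.1, Week 52 is close to nominal; at 0, nothing changes. For the visit models this rests on the literal reading. For the decline-rate model no other reading of the legible text is apparent. The stated sample size and power are unaffected. The SAP should be amended, but the point does not undermine the trial.

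**What to change.** **Week 52 and Week 72 models.** Replace the sole subject random effect with an unstructured within-subject covariance across visits. Pre-state the fallback order if it does not converge: heterogeneous Toeplitz, then heterogeneous AR(1). State the degrees-of-freedom method; Kenward-Roger is a reasonable default but matters little here.

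**Rate of decline.** Fit a correlated random intercept and random slope per subject. Pre-state that the random-intercept fit is reported, and flagged as such, if the slope variance is estimated at zero or the random-effects matrix is not positive definite.

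**Cost.** SAP wording and a small code change. Week 52 intervals widen by about 1% at slope SD 0, 4-7% at 0.1, 10-19% at 0.2, 17-29% at 0.3 and 31-41% at 0.5. Week 12 intervals narrow by 5-12% at 0.2 and 10-21% at 0.3. No unstructured fit failed in 45,000 Week 52 and 36,000 Week 72 simulated trials. The boundary rule for the random slope is needed: the fit reached the boundary in 55% of trials at slope SD 0, 25-43% at 0.1, 1-18% at 0.2 and 0-3% at 0.3. If an unstructured covariance was always intended, the visit-model change is one sentence.

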6.1.3.1 Model checking procedures

Handling of missing values/censoring/discontinuations

The primary analysis will be based on all subjects in FAS analysis dataset. There will be no imputation for the primary analysis based on mixed model repeated measurements (MMRM) for stimulated C-peptide AUC measurements at various visits, which is valid under the assumption that the missing data are missing at random (MAR).

6.1.3.2 Graphical presentation of results

Model estimated treatment geometric means and ratio between treatment and their 80% CI will be plotted over time, by visit.

6.1.3.3 Sensitivity analyses

If there are reasonable evidence that data may be missing not at random (MNAR), for example there are subjects discontinued study due to lack of efficacy or worsening of disease, alternative statistical model such as pattern mixture models may be used to evaluate the robustness of the primary analysis results.

6.2 Secondary objectives

The secondary objectives of this study are to evaluate the treatment effect of CFZ533 on full or partial remission, and to evaluate durability effects of CFZ533 over time on pancreatic beta cell function.

6.2.1 Variables

- Normalized stimulated C-peptide AUC_{0-2 hrs} by MMTT at Week 72.
- Average of Total daily dose of insulin

Total daily dose of insulin for a given day is the total daily units of insulin (adding insulin pump total basal units per day, insulin pump total bolus units per day and total units insulin injection (syringe) units per day) adjusted per body weight (unit/Kg/24 h). This information will be recorded at the site for at least 3 days and up to 7 days prior to each visit, as available (See Site Operations Manual). The average of total daily units of insulin per day (at each visit) will be calculated.

- Insulin-dose adjusted HbA1c (IDAA1c) ([Andersen et al 2014](#)).

IDAA1C = HbA1C (percent) + 4 × [insulin dose (units per kg per day)].

If HbA1c is stated in mmol/mol, it can be converted to percent by the following formula:
HbA1c % = (HbA1c mmol/mol × 0.0915) + 2.15.

- Remission at 52 weeks defined by meeting any of the below criteria:
 - Full remission defined by HbA1c ≤ 6.5% (48 mmol/mol) and no exogenous insulin use at 52 weeks.
 - Partial remission defined by Insulin Dose Adjusted HbA1c (IDAA1c) ≤ 9.0 ([Mortensen et al 2009](#))
 - Partial remission defined by HbA1c < 7.0% (53 mmol/mol) and total daily insulin dose < 0.5 units per kg per day ([Couper and Donaghue 2009](#)).
- The proportion of subjects with detectable C-peptide and time to undetectable C peptide. Undetectable C-peptide is defined as all timed values on the MMTT below the LLOQ.
- The proportion of subjects with Peak C-peptide ≥ 0.2 pmol/mL and time to Peak C-peptide < 0.2 pmol/mL (or below LLOQ)
- Rate of decline from baseline C-peptide

A linear mixed model regression of the log transformed stimulated C-peptide AUC, including baseline assessment, on time expressed in years (time = 1 at Week 52 and 0 at baseline) will be performed. The mixed model will include treatment effect, time by treatment interaction with time as continuous variable and subject as random effect. The estimates of the yearly rate of decline by treatment and their 80% confidence intervals will be obtained after back transformation (exponential) of the estimates of the slopes.

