Glycemic control is the most important factor for reducing the long-term microvascular complications in T1DM of retinopathy, nephropathy, and neuropathy as shown in the landmark Diabetes Control and Complications Trial (DCCT) (Diabetes Control and Complications Trial Research Group 1994, Steffes et al 2003). Yet, despite technological and clinical advances in the standard of care of T1DM, the majority of patients and particularly pediatric patients are not meeting glycemic targets. The mean glycated hemoglobin (HbA1c) level in adolescents was 9.0% (75 mmol/mol), well above guideline driven target for youth <7.5% (<58 mmol/mol) and close to levels in the 1980's (Miller et al 2015). T1DM patients with residual β -cell function, as measured by stimulated C-peptide > 0.2 nmol/L, achieve better glycemic control, are protected from severe hypoglycemia with insulin therapy (62% reduction), and have a 79% lower risk for progression of retinopathy and long-term complications (Diabetes Control and Complications Trial Research Group 1994; Steffes et al 2003). Therefore, therapies preserving residual β -cell function have potential to improve glycemic control and avoid serious short and long complications associated with T1DM.

[figure not shown]
T1DM disease onset and progression over the first year are markedly more aggressive in pediatric versus adult patients. Pediatric patients with new onset T1DM present with lower residual β -cell function at disease onset and a more rapid decline in remaining β -cell function over the first year when compared to adults. At 1 year of T1DM, pediatric patients lose about 50% of residual beta cell function while adults lose about 15% (Greenbaum et al 2012). Pediatric patients with new onset T1DM have more severe insulitis (inflammation of the pancreatic β -cells) with increased infiltration of B lymphocytes, including aggressive CD20+ B lymphocytes in pancreatic islets. Yet pediatric patients with new onset T1DM appear to be more responsive to immune modulatory interventions such as rituximab and teplizumab in randomized control trials (Woittiez and Roep 2015). Collectively, these observations support a

different pathobiology and disease kinetics between adults and pediatrics, such that interventions in one age group may not translate to the other in clinical trials.

Overview of auto-immune mechanisms in type 1 diabetes

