subjects eligible for a cohort open for enrollment will be randomized to receive either CFZ533 or placebo (2:1 ratio, stratified by age at first screening visit \geq 18 to 21 years and \geq 12 to $<$ 18 years) for one year, in addition to background standard of care with intensive insulin therapy,
Commercially Confidential Information

. In case of screening being extended, some screening procedures may need to be repeated, please refer to Site Operations Manual (SOM) for more information.

The treatment includes an initial loading dose of CFZ533 (administered at a dose of 30 mg/kg via a peripheral intravenous (IV) line
CCI on Day 1; all subjects receive the same dose in mg/kg) or matching placebo. All subjects will be observed for at least one hour following IV infusion to monitor for any untoward infusion-related adverse reaction. All subsequent doses of CFZ533 (or matching placebo), from Day 8
CCI

are administered on a weekly basis by subcutaneous (SC) injections at a dose which is based on body weight (details in [Section 4.2](#)). The last dose of the study drug is administered
CCI, and the end of the treatment assessment will be performed at Week 52.

A standardized liquid MMTT to assess β -cell function using C-peptide will be performed at baseline, Week 12, 24, 36, 52, and 72 (end of study), during the course of the study, as described in [Section 8.2.1](#). The following diabetes-related endpoints will also be monitored during the study: HbA1c,
Commercially Confidential Information

and diabetic ketoacidosis and hypoglycemic events. A study diary must be provided to subjects to report daily dose of insulin administration and glucose values
Commercially Confidential Information, whenever possible and for a period of at least approximately 3-10 days. At the baseline visit (prior to first dose),
CCI and instructed to start collecting data

3 to 10 days before the administration of first dose of study drug, with data collection intervals at:

- screening or baseline (prior to first dose),
- after receiving first dose of study drug,
- every 3 months (Weeks 12, 24, 36, and 52 or early drug discontinuation) during the first year of treatment,
- and Week 72 during follow-up, or early termination.
- Any subject enrolled in the study under an earlier version of the protocol which had longer follow up and who is beyond Week 72 when Clinical Study Protocol Amendment 6 is approved, will have an end of study visit at the next scheduled visit.

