12.8 Sample size calculation

12.8.1 Primary endpoint(s)

The sample size calculation is based on the primary endpoint of stimulated C-peptide AUC by the standard MMTT.

In [Greenbaum \(2012\)](#) the average baseline stimulated C-peptide AUC by MMTT is approximately 0.7 pmol*hr/mL. They show a linear decline in untreated subjects resulting in an average AUC of 0.4 pmol*hr/mL at one year. It is assumed that a clinically significant prevention of decline would occur if the rate of decline was one half (50%) of that of untreated subjects. Thus, a clinically relative improvement due to treatment would occur if the AUC at 1-year was 37.5% larger for treatment than placebo ($0.55/0.4 = 1.375$). Starting with 44 subjects and accounting for ~18% dropout rate, a total of 36 subjects randomized in a 2:1 ratio (stratified by age at first screening visit: ≥ 18 to 21 years, ≥ 12 to < 18 years) between CFZ533 and placebo provides 55% power to detect an improvement over placebo using a one-sided alpha=0.1 test when the true ratio of treatment to placebo is 1.375 (Note: if the rate of decline in treatment vs placebo is instead 75% less, corresponding to a ratio of 1.56, the power is 75%). This calculation assumes a coefficient of variation of 70% for the AUC; the standard deviation of log (AUC) was derived from the relationship between the CV and variance parameter for the lognormal distribution. This assumption was the result of the observed CV% of 5 TrialNet studies in T1DM subjects ([Bundy et al 2016](#)).

13 Ethical considerations and administrative procedures

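### The rate-of-decline model in SAP 6.2.1 leaves out the age stratum used in randomisation; adding age group by time is a free, low-priority improvement

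*SAP*

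**What the plan says.** Protocol Section 3 has subjects "randomized to receive either CFZ533 or placebo (2:1 ratio, stratified by age at first screening visit", with strata 18 to 21 and 12 to <18 years; the sample size section (12.8.1) repeats this.

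Three models of log C-peptide AUC are specified:

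- **Week 52 (SAP 6.1.3):** "Independent variables will include age group", together with treatment, visit, treatment by visit and log baseline AUC.
- **Week 72 (SAP 6.2.3):** the same model as the primary, so age group is in.
- **Rate of decline (SAP 6.2.1):** "The mixed model will include treatment effect, time by treatment interaction with time as continuous variable and subject as random effect". No age term is listed and no reason is given.

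On output, SAP 6.2.1 says: "The estimates of the yearly rate of decline by treatment and their 80% confidence intervals will be obtained after back transformation (exponential"). No between-arm slope contrast is named. Protocol 12.5.1 says these quantities "will be descriptively summarized with estimates and confidence intervals for each treatment group and each time point (where applicable").

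On age and decline, the protocol makes three statements. Section 1.1: "At 1 year of T1DM, pediatric patients lose about 50% of residual beta cell function while adults lose about 15" percent. Section 4.1, on randomisation, says the early rate of decline may differ at different ages. Section 4.1, on the age range, justifies the upper limit of 21 by reports that progression up to that age resembles that of adolescents.

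**The concern.** The stratum is dropped from the one C-peptide model that estimates decline, and decline is the quantity for which the protocol raises age as a possible source of difference. If slopes do differ between strata, two things follow. The between-stratum part of the slope variation stays in the error term, so the intervals do not benefit from the stratified design. And if the arms end up with different age mixes, each arm's rate reflects its own mix, so the two rates are not quite comparable. With 12 evaluable placebo subjects, a difference of one or two subjects is a visible share of the arm. The rates are likely to be read beside the design target, because Protocol 12.8.1 describes the effect of interest as a halving of the decline.

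**Working it through.** **The plan's own figure.** 12.8.1 assumes "a total of 36 subjects randomized in a 2:1 ratio" (24 vs 12), CV 70%, ratio 1.375 and one-sided alpha 0.1. SD of log AUC = √ln(1 + 0.7²) = 0.631. SE = 0.631 × √(1/24 + 1/12) = 0.223. Power = Φ(ln 1.375 / 0.223 − 1.282) = 55.8% (55.1% with the noncentral t), against 55% stated. At ratio 1.56 it is 76.1% (75.4%), against 75%. So the power reproduces, and it concerns Week 52 AUC. The documents give no figure for the decline model.

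**Assumptions for the decline model (not in the documents).** Residual SD 0.25 on the log scale; between-subject slope SD τ from 0 to 0.5; two thirds of subjects under 18; measurements at 0, 12, 24, 36 and 52 weeks; complete data; 24 vs 12.

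**Age gap in log slope, per year.**
- Lower bound 0 (Protocol 4.1, similar progression up to 21).
- Intermediate 0.25 (for example 50% vs 36% lost, since 0.50 × e^0.25 = 0.64).
- Upper bound ln 0.85 − ln 0.50 = 0.53 (the child-versus-adult losses of Protocol 1.1).

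**Interval width, closed form for a model with a random slope.** With time in years, the sum of squares about the mean time is 0.608, so the sampling variance of one subject's slope is 0.25² / 0.608 = 0.103. With ages balanced, the variance due to the age gap is gap² × (1/3)(2/3). Width with age group by time, relative to width without, is √[(τ² + 0.103) / (τ² + 0.103 + gap² × 2/9)].

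- Gap 0.53, τ = 0: √(0.103 / 0.165) = 0.79, or 21% narrower.
- Gap 0.53, τ = 0.5: √(0.353 / 0.415) = 0.92, or 8% narrower.
- Gap 0.25, τ = 0: √(0.103 / 0.117) = 0.94, or 6% narrower.
- Gap 0.25, τ = 0.5: √(0.353 / 0.367) = 0.98, or 2% narrower.
- Gap 0: no change.

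**Simulation, 2000 runs per setting, per-arm 80% intervals.**

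| Age gap | Random intercept only | Random slope as well |
|---|---|---|
| 0 | 0% | 0% |
| 0.25 | 1.5% to 1.7% narrower | 2% to 7% narrower |
| 0.53 | 5% to 7% narrower | 8% to 22% narrower |

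The closed form and the simulation agree to about one percentage point.

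**Which term does the work.** In a REML fit, adding age group as a main effect only, as in the primary model, left the slopes unchanged and moved their standard errors by less than 0.000002. Only age group by time acts on the slopes.

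**Age imbalance.** Under stratified 2:1 randomisation with assumed blocks of 3 or 6, the between-arm difference in age share averaged 0.01 to 0.04, with a maximum of 0.105. At the upper-bound gap the maximum shifts the slope difference by 0.105 × 0.53 = 0.056 log units per year, against an 80% half-width of about 0.17 for that difference. Two extra older subjects among 12 placebo subjects, which would take uneven dropout, give 2/12 × 0.53 = 0.09. At gap 0 every shift is zero.

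**Price of the extra terms.** With no age gap and balanced ages, width does not change. With no gap and a two-subject imbalance, per-arm widths rise by about 0.5% to 1.1%.

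**The case against.** The case for leaving the model alone has several sound parts.

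- A reader might infer from Protocol 1.1 that decline differs strongly between the two strata. The documents do not support that: the 50% and 15% compare children with adults, while both strata lie inside the range for which Protocol 4.1 reports similar progression. The 0.53 gap is an upper bound, not an expectation.
- A reader might infer that an uneven age mix passes straight into the slopes. Age is the stratification factor, so the mix is nearly even at randomisation. SAP Section 6 uses the full analysis set, so the visits that dropouts did attend stay in the model, which softens imbalance from dropout without excluding it.
- A reader might infer that the trial was sized on the decline rate. It was sized on the Week 52 AUC ratio; halving the decline only motivates the 1.375, and the model for that endpoint includes age group.
- A reader might conclude that the decline intervals are simply too wide. The SAP does not say whether the subject effect includes a random slope. If it is an intercept only, nominal 80% intervals covered about 70% at slope SD 0.3 and about 62% at 0.5 with no age gap, which is too narrow. That separate question matters more for interval validity, but settling it does not put the stratum into the model.
- Consistency with the primary model would supply only a main effect, which changes nothing here. Age group by time appears in no other specified C-peptide model.
- The rates are descriptive, and rate of decline is not in the endpoint tables (Protocol Table 2-1, SAP 1.3.1 and 1.3.2).

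Together these reduce the gain to somewhere between zero and modest. They do not supply a reason for omitting the stratum.

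**Conclusion.** The omission is real and unexplained: the trial randomises within age strata and adjusts for age group at Week 52 and Week 72, but not when it estimates the rate of decline. The size is small. Interval width is unaffected if progression is similar up to 21, about 2% to 7% wider than it need be for an intermediate age gap, and about 5% to 22% only if the child-versus-adult gap held between the strata. The slope shift from imbalance at randomisation is at most about 0.056 log units per year at that upper-bound gap; dropout or missing visits could add to it. All of this rests on the assumed slope and residual SDs, age mix and block sizes. The primary result is not touched. This is a free improvement of low priority.

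**What to change.** In the rate-of-decline paragraph of SAP 6.2.1, add age group (the randomisation stratum) and age group by time as fixed effects. Report each arm's yearly rate, with its 80% interval, at the pooled age-group proportions, using the same weights in both arms. A main effect alone would not serve the purpose. If the sponsor prefers to leave age out, one sentence giving the reason would close the point.

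The cost is a sentence or two in the SAP and two fixed-effect parameters. The data are already collected, and the only statistical price is about 1% of per-arm interval width if there is no age gap and the arms happen to be unbalanced.
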